2.5.3 Research Design and Group Allocation

This study will be a randomised control trial investigating the effect of a repeated practice listening to speech in the presence of a competing speaker on a variety of outcome measures. Participants will be randomly assigned to either the control or training group. Randomisation will be carried out using a dynamic adaptive allocation algorithm (Hoare et al., 2013) with an allocation ratio of 1:1. Two stratification variables will be used for the randomisation: age (<75 years : \geq 75 years) and sex (male : female). The experimental group will carry out the training programme detailed in Section 2.5.6 while the control group will be given a placebo intervention.

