2.5 Research Design

2.5.1 Participant Selection and Exclusion Criteria

This study will recruit existing hearing aid users attending for a reassessment appointment in the Wrexham Audiology service. They will have a need in their personal plan relating to improved speech perception in noise despite adequate aiding. Participants will have four-frequency average hearing thresholds greater than 20 dB HL. Participants will be recruited alongside a regular communication partner, either somebody who lives with them or who visits daily and is willing to complete the training programme with them. All participants (hearing aid users and communication partners) will also fulfill the following criteria: fluent and comfortable conversing in English, able to access the Wrexham Maelor Hospital Audiology Service, able to attend initial and followup appointments together, no significant self-reported memory problems or neurological problems. Participants should not have any reported colour-blindness. Participants will be aged between 65 and 85 years in order to reflect the main population of the BCU Audiology department. This is based on the mean age of patient attending for reassessment (75.37 years) \pm one standard deviation (13.19 years) rounded to 5 years. The inclusion of this criterion also helps to reduce the effect of ageing on results as it has been found that auditory training is more effective in younger people due to better neural plasticity (Baran, 2007). Any participants who do not meet these criteria will be excluded from the study.

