2.5.2 Sample Size

Based on the research design below an a priori sample size calculation has been carried out using the reported effect size of 0.8 on the QuickSIN from Olson et al. (2013). An effect size of 0.8 indicated that 25 participants are needed in each group to give a power of 80% at 5% significance.

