2.6.2 Measured Outcomes and Data Analysis

An ANCOVA will be used to assess any main effects of time or group on participants' performance on the QuickSIN, HHIE, Glasgow disability, MCRM or dual-task performance using initial performance on the QuickSIN as a covariate.

Table 2 Data to be collected during study

Data	Source
Age	At initial appointment from Auditbase
Gender	At initial appointment from Auditbase
Four-frequency average hearing levels	At initial appointment from Auditbase
Number of hearing aids (plus aided ear if	At initial appointment from Auditbase
unilateral fitting)	
Average hours of hearing aid use per day	At initial appointment from Auditbase
Initial HHIE	At initial appointment
Initial Glasgow disability	At initial appointment
Initial QuickSIN SNR loss	At initial appointment
Initial MCRM score	At initial appointment
Initial single task sore	At initial appointment
Initial dual task score	At initial appointment
Final HHIE	At final appointment
Final Glasgow disability	At final appointment
Final QuickSIN SNR loss	At final appointment
Final MCRM score	At final appointment
Final single task score	At final appointment
Final dual task score	At final appointment
Compliance	At final appointment from training diary

3 Project Considerations

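### The stated ANCOVA leaves out age and sex, the two factors that balance the allocation; if either is prognostic, standard errors are too large and some power is given up

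*Protocol*

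**What the plan says.** Protocol section 2.5.3 describes the allocation: "Randomisation will be carried out using a dynamic adaptive allocation algorithm", "with an allocation ratio of 1:1". It then states "Two stratification variables will be used for the randomisation: age" (under 75 against 75 and over) "and sex (male : female").

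Section 2.6.2 gives one ANCOVA for QuickSIN, HHIE, Glasgow disability, MCRM and dual task, "using initial performance on the QuickSIN as a covariate". Neither age nor sex is named as a model term there or elsewhere in the protocol, although Table 2 lists both among the data to be collected.

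Section 2.5.2 sets 25 per group "using the reported effect size of 0.8 on the QuickSIN", "to give a power of 80% at 5% significance". Section 2.5.1, when justifying the 65 to 85 age range, reports a finding that "auditory training is more effective in younger people due to better neural plasticity".

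**The concern.** Balancing on a factor removes most of the chance difference between arms on that factor. If the factor is related to the outcome, the treatment estimate varies less from trial to trial than under simple randomisation. A model without the factor does not register this: the factor's contribution stays in the residual variance and so in the reported standard error. Intervals come out wider than they need be, the test rejects less often than its nominal level, and precision that the design has already secured goes unused. With 50 participants planned, even a small gain is worth having if it costs nothing.

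**Working it through.** **Inputs.** From section 2.5.2: 25 per arm, effect 0.8 SD, 5% significance, 80% power. Two-sided testing is assumed; sidedness is not stated. From section 2.5.3: 1:1 dynamic allocation on two binary factors. From section 2.6.2: initial QuickSIN as covariate. I read the group comparison as final score on group plus initial QuickSIN. The protocol does not give R², the share of the variance remaining after initial QuickSIN that age and sex together explain. I take 0, 5, 10 and 20% as assumptions.

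**1. The plan's own figure.** n per arm = 2(1.960 + 0.842)² / 0.8² = 2 × 7.85 / 0.64 = 24.5, rounded up to 25. This reproduces the protocol. Power at 25 per arm is 80.7% by the normal approximation and 79.1% by the noncentral t. A one-sided calculation gives 20 and does not match.

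**2. Standard error.** Take the residual SD after baseline as 1 and n = 25.
- Reported by the stated model: √(2/25) = 0.283, whatever R² is.
- True, with the factors balanced: 0.283 × √(1 − R²).
- Ratio of reported to true: 1/√(1 − R²).

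At R² = 20% the true value is 0.283 × √0.80 = 0.253, so the reported one is about 12% too large.

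**3. Error rate and power.** The formula columns assume exact balance. The simulated columns use 50 participants, minimisation with an assumed 0.8 biased coin, each factor at 50% prevalence (assumed), additive effects, baseline in both models, and 4,000 trials per setting. Each pair is the stated model, then the model with age and sex added. Power is at 0.8 SD.

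| R² | SE ratio | Type I error, simulated | Power, formula | Power, simulated | Gain in points (formula, simulated) |
|---|---|---|---|---|---|
| 0% | 1.000 | 4.7%, 4.6% | 79.3%, 79.0% | 78.1%, 77.6% | −0.3, −0.5 |
| 5% | 1.026 | 4.4%, 4.8% | 79.9%, 81.0% | 78.0%, 79.4% | 1.1, 1.4 |
| 10% | 1.054 | 4.5%, 5.9% | 80.5%, 83.1% | 78.7%, 81.8% | 2.6, 3.1 |
| 20% | 1.118 | 2.9%, 4.6% | 81.9%, 87.2% | 79.3%, 85.0% | 5.3, 5.7 |

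In the simulation the mean reported standard error under the stated model stays at about 0.285 throughout, while the actual SD of the estimate at R² = 20% is 0.253 to 0.258. This agrees with step 2.

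**4. Simulation noise.** The Monte Carlo error of a 5% rate over 4,000 trials is √(0.05 × 0.95 / 4000) = 0.34 points. The 5.9% for the adjusted model is noise: in this simulation the adjusted model is correctly specified with normal errors, so its test has exact 5% size. A separate run of 20,000 trials per setting (24 per arm, balanced strata, no baseline covariate described) gave 4.8 to 5.0% for the adjusted test. The unadjusted test in that run gave 4.4, 4.0 and 2.7% at 5, 10 and 20%.

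**The case against.** The strongest objection is that the loss is conditional. A reader might infer that the trial's standard errors will be too wide and that power is lost. The documents do not support that: no figure shows that age or sex predicts any outcome once initial QuickSIN is in the model. At R² = 0 adjustment costs a fraction of a point. For QuickSIN itself R² may well be small, because its own baseline is already adjusted for and age is limited to 65 to 85. This objection stands, and it is why the size is given as a range.

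A reader might also take section 2.5.1 as proof that age is prognostic. It is not. The sentence concerns how well people respond to training, which is effect modification, whereas the calculation concerns a main effect on outcome. It shows only that age was considered relevant, and it does not compare those under 75 with those 75 and over. The protocol gives no prognostic rationale for sex.

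Two further inferences fail. The omission does not inflate type I error; the direction is conservative. It does not make the trial underpowered against its own target either: at 0.8 SD power under the stated model stays at 78 to 79% in simulation.

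Finally, a statistical analysis plan that is not shown could add the factors, and the sentence in section 2.6.2 does not call its covariate list complete. This has some force, but the protocol names the model and its covariate, so as written the balancing factors are out.

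**Conclusion.** The mismatch between design and stated analysis is plain in the text; the harm is conditional and probably modest. If age or sex predicts outcome beyond initial QuickSIN, the stated ANCOVA is conservative and forgoes about 1 to 2 points of power at R² = 5%, about 3 at 10% and 5 to 6 at 20%. The last is an upper scenario that nothing in the protocol supports. If neither factor is prognostic, nothing is lost. These figures assume 25 per arm, a 0.8 SD effect on the baseline-adjusted scale, additive effects and two-sided 5% testing. The sample size of 25 per group stands. The point is a free improvement, not a flaw that invalidates the test.

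**What to change.** In section 2.6.2, add the two balancing factors as covariates in the ANCOVA for every outcome: age, either continuous or as the under-75 / 75-and-over group, and sex. State which form of age is used, and settle it before outcomes are examined by arm.

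The cost is one phrase and two degrees of freedom (50 − 3 = 47 becomes 50 − 5 = 45). No new data are needed. If neither factor turns out to be prognostic, the price is about 0.3 to 0.5 points of power. Which baseline score each outcome should be adjusted for is a separate question that this change leaves open.

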2.5.4 Recruitment

A flow-chart detailing the recruitment pathway can be viewed in Figure 1. Potential participants and their communication partners will be identified by the Audiologist during

Figure 1 Recruitment pathway

their reassessment appointment. These participants will be given an invitation letter, the patient information sheet giving details of the study and exclusion criteria, an expression of interest form and a stamped addressed return envelope. If the patient replies that they do not wish to take part they will not be contacted again. If the patient and their communication partner are willing to participate and pass the exclusion criteria, a research appointment will be booked with the Principal Investigator or a Research Audiologist. If the patient's hearing aid has been exchanged but they do not require a hearing aid follow-up, a research appointment will be booked for them 8 weeks after their exchange appointment in order to allow time for acclimatisation to any hearing aid alterations. A poster will also be displayed in the waiting room of the Wrexham Audiology Department to alert patients to the existence of the research project.

2.5.5 Research Appointment Pathway

The research appointment pathway is shows in Figure 2. Participants and their communication partner will be asked to attend two 60 minute research appointments at the Wrexham Maelor Hospital Audiology Department. If possible, the first of these appointments will be linked to their hearing aid follow-up appointment (if required) as part of their Adult Hearing Pathway. The participant will be telephoned by the Principal Investigator at an agreed time two weeks after the initial research appointment to check on their progress. Any additional advice or support given during this telephone call will be noted by the Principal Investigator. The second research appointment will be arranged four weeks after the initial appointment in order to complete the final assessment.

The participant's general hearing aid follow-up and their initial research assessment will be completed separately if they are booked to coincide. Once the follow-up appointment is concluded, including completion of the patient's Personal Plan, the participant will be given a five minute break before the initial research assessment will begin.

At the start of the initial research assessment the content of the study will be explained and informed consent obtained. Three copies of the consent form will be completed; one for the participant's own records, one which will be scanned and added to the Audiology Patient Management System (Auditbase), and one copy which will be kept in a locked cabinet in the Principal Investigator's office at Wrexham Maelor Hospital for a period of six months following the end of the study. A subjective listening check of the participant's hearing aid/s will be carried out to ensure that it is functioning correctly.

Figure 2 Research Appointment Plan

The participant will then complete the HHIE and Glasgow disability question. Their SNR loss will be measured using the QuickSIN and they will then complete the MCRM and dual task. The participant and their communication partner will be given a full explanation of the training programme or placebo programme, given the training workbook and will be provided with the CD containing the noise or placebo stimulus and the compliance letter. They will also be given the training diary to complete at home.

The final research appointment will take place four weeks after the initial research assessment. During this appointment the outcome measures of QuickSIN, HHIE, Glasgow disability, MCRM and dual task will be completed in order to obtain final performance on these measures. The participant and their significant other will also be given a questionnaire to obtain their feedback on the training programme.

2.5.6 Training Programme

The training programme used in this study will focus primarily on improving speech perception in noise. Participants will have a conversation with their communication partner in the presence of a single competing speaker presented in soundfield for 30 minutes, five times per week for four weeks. The training schedule used in this study is based on the well documented regimen used in the LACE training programme. The single-talker distractor will be formed of a selection of 30 minute extracts from four English language commercially available audiobooks. A range of male and female distractors will be used. A single-talker distractor has been chosen as studies have shown that the informational masking from an intelligible single-talker has a greater effect on performance than the energetic masking from speech-shaped noise (Brungart, 2001). These extracts will be recorded onto a CD which will be provided to the participants in order for them to complete the training programme at home. At the end of each 30 minute extract a tone will sound to alert the participant that the training session for that day is complete. Participants will be instructed to play the CD at a level which is challenging but comfortable (i.e. not too loud).

As previously stated, compliance for clinically administered auditory training programmes has previously been low. In order to improve compliance a spoken letter will be given to the participants after the tone at the end of their training session. An incentive will be given to participants completing the training programme by being entered into a prize draw to win £25 book tokens for gathering all of the letters.

The placebo training programme undertaken by the control group will involve the same period of training but in quiet. They will be given a blank CD which is segmented into 30 minute sections with the tone and compliance letter given at the end of the training session.

All training, placebo and intervention, should be carried out while the participant is wearing their hearing aid/s. If the participant has multiple programs for different listening environments they should complete the training while listening in the program most suited to the training situation i.e. everyday listening for the control group and background noise for the experimental group.

2.5.7 Involvement of Service Users in Study Materials

Current service users were consulted on the concept and design of the study. All documentation to be provided to participants has been reviewed by users to ensure that it is clear and understandable and their comments have been incorporated.

2.5.8 Tools to be Used

All aspects of research appointments will be in addition to routine appointments that hearing aid patients would have attended. Research appointments will include the following components which will be carried out for all participants:

• Research introduction and consent – approximately 5 minutes at initial research assessment

A full explanation of the purpose of and procedure for the study will be provided and participants will be given the opportunity to ask questions. Potential participants will be informed that they can withdraw from the study at any time, without offering an explanation or affecting their ongoing care. If they are willing to participate, a written consent form will be signed by the patient.

• *Otoscopy* – approximately 2 minutes at both research appointments

Bilateral otoscopy will be carried out to ensure that participant's ears are healthy and clear of wax. If wax removal is required then this will be arranged on the day.

• Hearing aid listening check – approximately 5 minutes at both research appointments

A listening check will be performed on the participant's hearing aid/s to ensure that they are functioning correctly.

- Self-report approximately 10 minutes at both research appointments
 - Hearing Handicap Inventory for the Elderly
 The HHIE will be administered in written form. Participants will be provided with the questionnaire and asked to mark their answer of "Yes", "No" or "Sometimes" in the relevant box. Their questionnaire will be scored by the researcher
 - Glasgow Disability

Participants will be asked the disability question of the Glasgow Hearing Aid Benefit Profile Part 1 for situation 4 (Having a conversation with several people in a group) only. This will be provided in written form and they will be asked to rate their difficulty level as "No difficulty", "Only slight difficulty", "Moderate difficulty", "Great difficulty" or "Cannot manage at all". Their response will be recorded by the researcher.

• Speech intelligibility testing – approximately 10 minutes at both research appointments

Three QuickSIN lists will be administered in the soundfield while the participant is wearing their hearing aids. The stimulus will be set to a level which is reported to be comfortable by the participant. Different lists will be administered at the initial appointment and final appointment. Participants will be required to repeat back the sentence which they have heard and the researcher will record how many keywords were repeated accurately. The QuickSIN will be scored by the researcher.

- Cognitive measures approximately 20 minutes at both research appointments
 - MCRM

The MCRM will be administered using Matlab. The level of the stimulus will be set to a level which is comfortable for the participant. The participant will be presented with the visual display represented in Figure 3 and will use the mouse to select the appropriate number-colour combination. Speech reception thresholds (SRT) are measured using an adaptive 1-up 1-down staircase method consisting of eight reversals. The SRT is calculated based on the average of the last two reversals.

Figure 3 Visual display for participant response during MCRM task

Dual task

This test will be administered using PsychoPy. The stimulus level will be set by the participant at a level which is comfortable. The word task will initially be presented in isolation in order to establish single task performance. Participants will be required to immediately repeat the words that they heard and these will be scored by the researcher. The word task will then be administered sandwiched between the digit task to measure dual task performance. Participants will type the numbers that they recall using the keyboard. Four word lists will be presented in both the single and dual task conditions. The single and dual tasks will be administered twice at the initial appointment to allow for practice however only the second administration will be scored. In the single task there is a maximum possible score of 20 correct words. In the dual task there is a maximum possible score of 20 correct words and 20 correct digits. The dual task score is calculated by summing the total correct words and digits. The dual task decrement will be calculated by comparing performance on the single and dual task.

Introduction to training programme and issue of training materials – approximately
 20 minutes at initial research appointment

The participant and their communication partner will be given verbal instructions giving details of all aspects of the training programme. They will be issued with written instructions and a copy of the training CD. Participants in the experimental group who will

be undertaking training in noise will practice setting the level of the distractor to an appropriate level.

• Feedback questionnaire – approximately 5 minutes at final research assessment Participants will complete the written feedback questionnaire in order to obtain their opinion of the training programme. This includes questions on the ease of undertaking the programme, and any changes that they would recommend for future. The questionnaire has been adapted from one commonly used during research at the NIHR Nottingham Hearing Biomedical Research Unit.

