1.2 Project Personnel and Collaborators

The Principal Investigator will complete initial planning, invite participants to participate in the project, manage all assessment and final appointments, analyse the data, write the initial report and disseminate the results.

The first co-applicant will contribute to initial planning, provide support for the application, provide advice on managing all financial aspects, provide advice on other clinical and research aspects, and contribute to the write-up and dissemination of results. The second and third co-applicants will provide support to the research design and write-up. Audiologists from the Wrexham Maelor Hospital Audiology Department will assist with data collection and highlighting possible participants to the Principal Investigator.

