4.3 Impact of Research on Normal Workload

This study forms part of a clinical training programme for the Principal Investigator whose time is externally funded. Therefore, the time spent by the Principal Investigator on this project is not included in the summary of costs.

Data collection is expected to take 100 hours of clinical time. Research Audiologists will be involved in data collection, undertaking three-quarters of the total research appointments (the remaining quarter will be covered by the Principal Investigator). Part of the funding for this research will be used to backfill lost clinical sessions. The cost of the

02/09/13 30/09/13 28/10/13 25/11/13 23/12/13 20/01/14 17/02/14 17/03/14 14/04/14 12/05/14 09/06/14 07/07/14 04/08/14 01/09/14 29/09/14

Figure 4 Gantt chart showing timescale of project

Table 3 Costs involved in the research project

	Cost (£)	Justification
Staff costs	1753.73	 Backfill of clinical time lost through project: Mid-point Band 6 Audiologist, 75 hours x £18.77 including on-costs Mid-point Band 8 Audiologist, 10.5 hours x £32.95 including on-costs As completion forms part of a clinical training programme for the Principal Investigator all time spent on aspects of the project are covered under the terms of the training programme and are therefore not included in the staff costs. NHBRU staff researchers' time is funded by the NIHR.
Materials and consumables	115	Stationary (paper, envelopes etc.): £12.50 Postage: £37.50 Recordable CDs: £40 Voucher for prize draw: £25
Travel	1420	Travel costs for additional journeys undertaken by research participants: 25 participants with 1 additional journey, £10 per journey 25 participants with 2 additional journeys, £10 per journey Travel for meetings between researchers £670
Apparatus and	125	Purchase of QuickSIN
Total	3413.73	

additional workload generated by this study have been included in the above research costs (see Table 3).

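### Nothing in the protocol keeps the person who scores the final QuickSIN and spoken words by ear from having issued, coached or supported the programme

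*Protocol*

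**What the plan says.** **Scoring.** In Section 2.5.8 the participant repeats QuickSIN sentences aloud and "the researcher will record how many keywords were repeated accurately. The QuickSIN will be scored by the researcher". The word task, alone and within the dual task, works the same way: "Participants will be required to immediately repeat the words that they heard and these will be scored by the researcher". The MCRM response is made with the mouse and the recalled digits are typed.

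**Who learns the arm.** Section 2.5.5 places programme delivery at the initial appointment, after baseline testing. The participant and partner are "given a full explanation of the training programme or placebo programme, given the training workbook" and the CD. Under Section 2.5.8, only the experimental group then practises setting the distractor level. Whoever runs that visit therefore knows the arm.

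**Mid-trial contact.** Section 2.5.5: "The participant will be telephoned by the Principal Investigator at an agreed time two weeks after the initial research appointment". Any advice or support given on the call is noted.

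**Staffing.** Section 1.2 says that the Principal Investigator will "manage all assessment and final appointments, analyse the data, write the initial report and disseminate the results". Section 4.3 describes Research Audiologists "undertaking three-quarters of the total research appointments (the remaining quarter will be covered by the Principal Investigator"). Section 2.5.4 books the research appointment with either role. None of these sections divides the work into initial and final visits.

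**Masking.** No section of the text mentions a masked assessor, a separate final-visit scorer or re-scoring from recordings. Section 3.2 lists limitations of selection, motivation and control of training, but not unmasked scoring.

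**The concern.** The protocol builds a careful placebo arm: same duration, a CD, a tone and compliance letters. It then leaves the scorer free to know which arm the participant is in. A scorer who hears an unclear word from a participant known to have trained may give the benefit of the doubt more often than for a control.

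Such leniency at the final visit would enter the group difference directly. The baseline QuickSIN is taken before the programme is issued, so it carries none of this bias. Adjusting for it in the ANCOVA therefore cannot take the bias out, and only narrows the interval around a shifted estimate.

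QuickSIN is nowhere formally labelled the primary outcome. It is the speech-in-noise measure that corresponds to the primary aim in Section 2.1, and the sample size in Section 2.5.2 is built on it, so this is where the trial's main conclusion will rest. Who scores, and what that person may know, is trial conduct that the protocol itself settles. It is not a matter normally left to a statistical analysis plan.

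**Working it through.** **1. The plan's own figure.** Section 2.5.2 gives an effect size of 0.8, 80% power, 5% significance and 25 per group. Assuming a two-sided test, the normal formula is n = 2 × ((1.960 + 0.842) / 0.8)² = 24.5, rounded up to 25. The figure reproduces, with power 80.7% by the normal approximation and 79.1% by the t-test. Masking the scorer does not change it.

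**2. How much is judged by ear.** Three lists per visit (Section 2.5.8) × six sentences × five key words (Section 2.2.3) = 90 keyword judgements at each final visit. The word task adds up to 20 words in the single condition and 20 in the dual condition.

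**3. Who could know the arm at the final visit.**
- If Section 1.2 is read literally, the Principal Investigator is responsible for every initial and final appointment, makes the support calls and analyses the data.
- If Section 4.3 is followed, the Principal Investigator takes a quarter and Research Audiologists take the rest. Any of them may take either visit, and may take both for the same participant.

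On either reading, nothing separates delivery or support from scoring.

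**4. Illustration of size.** The protocol gives no scorer-bias figure, no QuickSIN SD and no baseline correlation, so all three are assumptions. Let the shift favouring training be b SD, with no true effect and 25 per arm. The two-sided rejection rate is the power of a two-sample t-test at effect b. With a baseline correlation of 0.7, the residual SD is √(1 − 0.7²) = √0.51 = 0.714, so the effect becomes b / 0.714.

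| Assumed shift b | No covariate | Effect with correlation 0.7 | Rejection rate with correlation 0.7 |
|---|---|---|---|
| 0 | 5.0% | 0 | 5.0% |
| 0.1 SD | 6.4% | 0.14 | 7.7% |
| 0.2 SD | 10.7% | 0.28 | 16.3% |
| 0.3 SD | 18.0% | 0.42 | 30.7% |

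A shift of 0.2 SD is 0.2 / 0.8 = one quarter of the planned effect.

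**5. Whether roles can be separated within the stated staffing.** 50 participants × 2 visits of 60 minutes = 100 appointments, which matches the 100 hours in Section 4.3. Three-quarters is 75, which matches the 75 Band 6 hours in Table 3. If the Principal Investigator's 25 are all initial visits, Research Audiologists do 25 initial + 50 final = 75. The split and the budgeted hours are unchanged.

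**The case against.** **Same person at both visits.** A reader might infer that the person who issues the programme is the one who scores that participant at the end. The documents do not say so. For Research Audiologists the overlap is possible but not stated, and the two-week call belongs to the Principal Investigator alone. The research appointment plan figure is not shown, so it could not be checked. What stands is that the text does nothing to prevent overlap.

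**Constrained scoring.** Each sentence has five fixed key words, each recorded as repeated accurately or not, and Section 2.5.9 provides refresher training in the tests. This limits discretion. It does not mask the scorer.

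**Re-rostering as a cure.** A reader might take a new roster to remove the bias. It would not. The two programmes are easy to tell apart, and Section 2.5.1 requires the partner to attend both appointments, so two people could reveal the arm.

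**The percentages.** They should not be read as estimates for this trial. The shift and the correlation are both assumed, the upper figures need both to hold together, and without an SD the shift cannot be converted into keywords out of 90. They show sensitivity only.

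**Sections 1.2 and 4.3.** The role in Section 1.2 could be meant as oversight, and that section also has departmental audiologists assisting with data collection. That would soften the conflict but still leave open who scores.

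**Conclusion.** The concern holds as a gap in design: following the protocol as written, someone who knows the allocation may score the final QuickSIN and the spoken words. The finding rests on the text and not on any calculation. Its size in this trial is unknown. Under the assumptions shown, the false-positive rate would be about 6% to 18% without a covariate and 8% to 31% with an assumed baseline correlation of 0.7, against a nominal 5%. The self-completed questionnaires, the MCRM and the typed digits are less exposed to scorer judgement. Separately, Sections 1.2 and 4.3 give different accounts of who runs the appointments and must be reconciled. The change is worth making because the exposure falls on the key outcome and the remedy fits the existing staff hours.

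**What to change.** Within the existing 75/25 split:
- Roster the Principal Investigator's 25 appointments as initial visits only. This also keeps the person who makes the support calls away from final scoring.
- Have each final visit done by a Research Audiologist who did not see that participant initially and is not told the arm.
- Complete all outcome tests before the diary and feedback questionnaire are handed over.
- Ask participants and partners not to describe their programme to the assessor.
- Amend Sections 1.2, 2.5.5, 2.5.8 and 4.3 so that they agree on this.

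**Cost.** Sample size, appointment count and budgeted hours stay as they are. Booking becomes less flexible. At least two Research Audiologists must be available throughout: the protocol uses the plural but gives no number, so this needs confirming. Some unmasking will remain.
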